with Ad26.COV2.S on coagulation-related parameters:	• Hematology assessments of complete blood count with differential, including platelet
• In the event of a suspected adverse event of special interest (AESI) of thrombosis	counts (performed locally at the site: see Section 6.2). $^{(1)}$
with thrombocytopenia syndrome (TTS),	• Analysis of levels of pro- and anti-
tested retrospectively in samples obtained	coagulation factors in plasma/serum
from pregnant participants at baseline (Day 1, pre-dose) and at 7 days, 14 days	thromboplastin time, prothrombin time,
and 28 days after vaccination, and	fibrinogen, D-dimer levels, Lupus anticoagulant, ant-cardiolipin antibody
which these coagulation factors correlate	levels, β -2 glycoprotein, anti-PF4 antibody levels (performed retrospectively at central
with platelet counts as determined at the time as part of the standard hematology	laboratories on stored samples) (see Section 6.2) $^{(1)}$
safety assessment of complete blood count (CBC), will be determined.	
• Coagulation-related parameters (including pro-and anti-coagulation	
factors) and the extent to which these fluctuate pre and post vaccination with	
Ad26.COV2.S, will be determined for a subset of participants.	
To assess SARS-CoV-2 viral load in SARS-	Analysis of SARS-CoV-2 viral load (via
CoV-2 infected participants during a confirmed COVID-19 episode.	qRT-PCR) in nasal swabs collected during a confirmed COVID-19 episode. ⁽¹⁾
To explore changes in the SARS-CoV-2	• Identification of SARS-CoV-2 variants by
genome	sequencing of nasal swabs samples (as available). ⁽¹⁾

Objectives	Endpoints	
Neonates and Infants		
To assess the occurrence of symptomatic molecularly confirmed COVID-19 and	• The number of neonates/infants with molecularly confirmed COVID-19. ⁽¹⁾	
severity of COVID-19 signs and symptoms in neonates/infants of adult participants who have received Ad26.COV2.S during the 2 nd and/or 3 rd trimester of pregnancy.	• Presence and severity of COVID-19 signs and symptoms as measured by the Pediatric Symptoms of Infection with Coronavirus-19 (PedSIC).	
To assess the occurrence of asymptomatic SARS-CoV-2 infection in neonates/infants born to adult participants who have received Ad26.COV2.S during the 2 nd and/or 3 rd	• The number of neonates/infants with positive non-S protein ELISA and/or SARS-CoV-2 immunoglobulin assay (eg, N-protein ELISA).	
trimester of pregnancy.	• Asymptomatic infection detected by RT- PCR.	

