5. STATISTICAL ANALYSES

5.1. General Considerations

A baseline (or reference) value will be defined as the value of the last available assessment prior to the first vaccination on Day 1, where Day 1 is the date of first vaccination for adults. A value at birth is baseline value for neonates and the birth date is the neonate reference date. The neonate baseline values for immunogenicity analysis are those from the cord blood sample collected.

Every adult will have a unique subject ID in the ADaM datasets and every neonate will have the same unique subject ID with 'A' added at the end of the ID. Multiple pregnancies [twins or higher order multiples] are excluded from the study but if a participant with multiple pregnancy is inadvertently enrolled, neonates will have the same unique subject ID with 'A', 'B', 'C' and D added at the end of the ID based on the number of neonates.

Unless otherwise specified, continuous variables will be summarized using the following statistics, as appropriate: number of observations, arithmetic mean (mean), standard deviation (SD), standard error (SE), median, minimum, and maximum. Frequencies and percentages (one decimal place) will be generated for categorical variables. Denominator for the percentages is the number of participants in the considered population, and phase (where applicable; incidence per 100 participants/phase).

No formal statistical testing is planned. The safety analysis will be performed on the FAS-A based on actual intervention received and the FAS-NVN, unless otherwise specified. Safety data will be presented by period/phase (as applicable) as well as over the entire study. Immunogenicity results will be conducted on the PPI-A and PPI-NVN and presented per scheduled time point as appropriate. Safety and immunogenicity endpoints will be summarized descriptively by previous vaccination group (as defined in Section 1.2) and overall. All listings will include the previous vaccination group. Vaccination schedule in Group 4 (i.e. vaccine-naive at study entry) will have two components: the Primary Vaccination and the (optional) Booster Vaccination. Listings will be shown per phase and time point, as appropriate.

Participants that took another COVID-19 vaccine during the study are excluded from all safety and immunogenicity analyses from the moment they received the other vaccine. The safety data from those participants after they received the other vaccine will be listed separately.

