- Passive transfer: analysis of immune mediators correlating with protection against experimental SARS-CoV-2 challenge in a suitable animal model
- Analysis of binding and/or neutralizing antibodies against emerging SARS-CoV-2 variants

Occurrence of symptomatic molecularly confirmed COVID-19 and severity of COVID-19 signs and symptoms in adult participants

- The number of adult participants with molecularly confirmed COVID-19
- Presence and severity of COVID-19 signs and symptoms as measured by the Symptoms of Infection with Coronavirus-19 (SIC)

Assessment of SARS-CoV-2 viral load during a confirmed COVID-19 episode in adult participants

• Analysis of SARS-CoV-2 viral load (via qRT-PCR) in nasal swabs collected during a confirmed COVID-19 episode

Changes in the SARS-CoV-2 genome in adult participants

• Identification of SARS-CoV-2 variants by sequencing of nasal swabs samples (as available)

Occurrence of symptomatic molecularly confirmed COVID-19 and severity of COVID-19 signs and symptoms in neonates/infants

- The number of neonates/infants with molecularly confirmed COVID-19
- Presence and severity of COVID-19 signs and symptoms in neonates/infants as measured by the Pediatric Symptoms of Infection with Coronavirus-19 (PedSIC)

Assessment of SARS-CoV-2 viral load during a confirmed COVID-19 episode in neonates/infants

• Analysis of SARS-CoV-2 viral load (via qRT-PCR) in nasal swabs and/or saliva samples (as available) collected during a confirmed COVID-19 episode

Occurrence of asymptomatic infections with SARS-CoV-2 in adult participants

- The number of adult participants with positive non-S ELISA and/or SARS-CoV-2 immunoglobulin assay that is dependent on the SARS-CoV-2 nucleocapsid (N) protein
- Asymptomatic infection detected by RT-PCR

Occurrence of asymptomatic SARS-CoV-2 infection in neonates/infants

- The number of neonates/infants with positive non-S protein ELISA and/or SARS-CoV-2 immunoglobulin assay (eg, N-protein ELISA)
- Asymptomatic infection detected by RT-PCR

Impact of Ad26.COV2.S vaccine on the incidence of co-infections with SARS-CoV-2 and other respiratory pathogens in adult participants

• Analysis of broad respiratory pathogens panel in the nasal swabs collected during a confirmed COVID-19 episode and in a subset of nasal swab samples from adult participants with a symptomatic infection, up to delivery

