5.7.1.5. Immunogenicity Against the Insert

5.7.1.5.1. Humoral Assays

For **VNA** (both wild-type virus and pseudovirion expressing S protein, as available), the following statistics will be calculated: N, geometric mean, and corresponding 95% CI of the actual values, fold change from baseline and fold change from pre-booster (for time points after booster vaccination). In some cases, fold change from other timepoints may also be calculated. Geometric mean ratio and CI will be calculated at each post baseline visit.

For the calculation of the geometric mean and its corresponding 95% CI, the arithmetic mean, and its corresponding 95% CI are calculated on the log₁₀ transformed values. These values are back transformed to provide the geometric mean and its corresponding 95% CI.

For wild-type and pseudovirion VNA separately:

- A sample will be considered positive if the value is strictly greater than the LLOQ (>LLOQ).
- Responder definition (in adults): A post-baseline sample will be considered a responder if at least one of the following conditions is satisfied:
 - $\circ~$ The baseline sample value is less than or equal to the LLOQ (\leq LLOQ) and the post-baseline sample value is strictly greater than the LLOQ (>LLOQ)
 - The baseline sample value is strictly greater than the LLOQ (>LLOQ) and the post-baseline value represents an at least 4-fold (\geq 4-fold) increase from the baseline sample value.

Actual values are tabulated and shown as dot plots with dots for participant values, and the corresponding geometric mean and 95% CI per time point for each assay. In addition, GMT plots over time without individual participant dots will also be generated. Participant profiles of the actual values over time will be graphically presented.

For infants born to vaccinated mothers, tables and graphs will be made per the vaccine regimen of the mother. In addition, in the neonate profiles of the actual values over time, the mother's value at birth will be added to visualize transfer of binding or neutralizing antibodies to the newborn.

In the graphs, original values will be displayed on the log_{10} scale.

Further details and/or updated rules will be provided in the DPS.

For the exploratory **variant SARS-CoV-2 neutralization assays** (different from the VNA used for the secondary endpoint), the same as above applies.

For **S-ELISA** and **MSD 4-PLEX**, the same as above applies.

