5.7.2. Occurrence of Symptomatic Molecularly Confirmed and Asymptomatic COVID19

An immunologic test for SARS-CoV-2 seroconversion (non-S ELISA and/or SARS-CoV-2 immunoglobulin assay) based on SARS-CoV-2 N-protein, will be performed in adult participants to identify cases of asymptomatic infection. The presence of SARS-CoV-2 infection will be assessed at the study site by molecular testing RT-PCR or molecular test result from any available respiratory tract sample. Asymptomatic infections also include those detected by confirmed molecular tests (either in this study or outside study), in the absence of the relevant symptoms.

Procedures to be performed in the event a participant (adult or infant/neonate) experiences signs or symptoms suggesting possible COVID-19 are detailed in CTP Sections 1.3 and 8.1.2. A sign or symptom is considered as absent or present for a COVID-19 episode if observed in the eCOA or eCRF for the COVID-19 episode, and absent if not.

COVID-19 episodes will not be adjudicated. All data presented corresponding to the COVID-19 episode will be based on the SIC (or PedSIC) as detailed in Section 5.7.3.

The following analyses will use the FAS-A set and will be conducted at the time of the final analysis:

The number and percentage of participants with at least one molecularly confirmed symptomatic or asymptomatic SARS-CoV-2 infection will be tabulated by post vaccination visit and for the entire study period. Similar table will be produced for infants.

The number and percentage of participants who are positive by N serology at different time points will be tabulated.

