5.7.5. Definition of Subgroups

For key safety and immunogenicity analyses (S-ELISA, MSD 4-plex and VNA), results will be analyzed by gestational age group at screening and by SARS-CoV-2 serostatus at baseline. Results will be presented by previous vaccination group like other reports.

Subgroups are defined as shown in Table 6 while the derivation of the SARS-CoV-2 Serostatus at baseline is described in Table 7.

Subgroup analysis will ignore unknown, missing and not reported values, unless otherwise specified.

Subgroup	Definition
(at baseline/screening)	
Age Group	• 18-34 years (≥18y to <35y)
	• 35-45 years (≥35y to ≤45y)
Gestational Age Group	• 16-27 weeks (≥16w to <28w)
	• 28-38 weeks (≥28y to ≤38w)
BMI	• underweight $<18.5 \text{ kg/m}^2$
	• normal $18.5 - <25 \text{ kg/m}^2$
	• overweight and obese $>=25 \text{ kg/m}^2$
Race	• Asian
	Black or African American
	• White
	• Other ('Multiple ^a or 'Native Hawaiian or other Pacific Islander' or
	'American Indian or Alaska Native')
Ethnicity	Hispanic or Latino
	Not Hispanic or Latino
SARS-CoV-2 Serostatus	• Negative
	 Not Negative (excluding missing)

Table 6:	Definition	of Subgroups
		0 1

^a If multiple race categories are indicated, the Race is recorded as 'Multiple'.

Vaccination history	SARS-CoV-2 Serostatus at baseline (by N and/or S serology for vaccine naïve, and by N-serology for previously vaccinated individuals) to assess previous infections	Serostatus result at Baseline
Vaccine naïve (Group 4)	If positive in either Roche Elecsys (N serology) or S-Elisa, or both	Positive
	If negative in both	Negative
	If both are missing	Missing
Other vaccines (and no inactive vaccine) based on S protein	If positive by Roche Elecsys (N serology) only (regardless of the S-ELISA result)	Positive
(Moderna, Pfizer, AstraZeneca, Janssen, Sputnik, Novavax)	If negative by Roche Elecsys (N serology) only (regardless of the S-ELISA result)	Negative
	If Roche Elecsys (N serology) is missing (S- ELISA is not used here)	Missing
Others; depends on vaccine		
Inactivated vaccines (e.g. Sinovac, Sinopharm) or combination of vaccines including at least one inactivated vaccine	Since participant is previously vaccinated with an inactivated vaccine, it is not possible to determine serostatus at baseline	Not evaluable

 Table 7:
 Definition of SARS CoV 2 Serostatus at Baseline

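### The infant asymptomatic-infection endpoint counts any N-seropositive infant as infected, with no rule to set aside antibody acquired from the mother

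*SAP*

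**What the plan says.** Section 5.5.1, under the heading "Occurrence of asymptomatic SARS-CoV-2 infection in neonates/infants", lists two measures. The first is "The number of neonates/infants with positive non-S protein ELISA and/or SARS-CoV-2 immunoglobulin assay (eg, N-protein ELISA"; the second is infection detected by RT-PCR. The exploratory objectives in Section 1.1 carry the same pair, introduced by "To assess the occurrence of asymptomatic SARS-CoV-2 infection in neonates/infants". The serology measure names no time point, comparison sample or maternal condition.

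Other sections bear on how an infant antibody result should be read:

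- **Section 5.7.1.5.1:** in infant profiles over time, "the mother's value at birth will be added to visualize transfer of binding or neutralizing antibodies to the newborn".
- **Section 5.1:** "The neonate baseline values for immunogenicity analysis are those from the cord blood sample collected".
- **Section 5.5.1, adult humoral list:** anti-N antibody is among the possible analyses in adults' peripheral and cord blood.
- **Section 5.7.5, Table 7:** mothers may be positive by N serology at baseline.
- **Section 5.7.2:** N serology is described as a seroconversion test, for adults only. It adds "The number and percentage of participants who are positive by N serology at different time points will be tabulated", for analyses on the FAS-A.
- **Section 5.7.3.2:** one table of positive N-ELISA is limited to participants seronegative at baseline.

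**The concern.** Anti-N antibody in a newborn or young infant has two possible sources: the infant's own infection, or antibody received from a mother who was infected. The endpoint treats both as infant infection. The SAP accepts that binding antibody reaches the newborn and that some mothers will be N-positive, so the second source is foreseeable from its own text.

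The result would be labelled as infection in infants of vaccinated mothers, while part of it would reflect how many mothers had been infected. A reader could take it as infection despite maternal vaccination. Because the misclassification can only add cases, it does not average out.

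**Working it through.** **Step 1: look for a rule elsewhere in the SAP.**

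- Section 5.5.3 sends this endpoint to Section 5.7. Within that, Section 5.7.2 describes N seroconversion for adults only. Its statement that a similar table will be made for infants follows the sentence on molecularly confirmed infection, so it is not an N-serology rule.
- The baseline-seronegative restriction in Section 5.7.3.2 relies on serostatus, which Table 7 defines by the participant's vaccination history. Infants have none. If the vaccine-naïve row were applied to them, a positive S-ELISA in cord blood would make the infant positive, so antibody passed on from a vaccinated mother would remove infants from the seronegative group.
- The end of Section 5.7.5 reports infant results by the mother's subgroup at baseline or screening. That covers immunogenicity analyses only and misses maternal infection between enrolment and delivery.
- Section 5.1 makes cord blood the neonate baseline for immunogenicity, but the infection endpoint does not use it.

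No section separates maternal antibody from the infant's own response.

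**Step 2: illustrate the size.** The SAP gives no rate or precision for this endpoint, so there is no figure to reproduce. All three inputs below are assumptions:

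- m, share of mothers N-positive at delivery: 10-50%
- t, share of their infants still N-positive from maternal antibody at sampling: 5-90%
- q, true infection among infants: 2-5%

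Take maternal antibody and infant infection as independent, and every true infection as seropositive. Then:

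- counted = 1 − (1 − q)(1 − m × t)
- false positives = m × t × (1 − q)

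For m = 30%, t = 50%, q = 2%: m × t = 0.15; counted = 1 − 0.98 × 0.85 = 0.167; false = 0.15 × 0.98 = 0.147.

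| m | t | q | Counted per 100 | False per 100 | False share of count |
|---|---|---|---|---|---|
| 10% | 5% | 5% | 5.5 | 0.5 | 9% |
| 10% | 50% | 5% | 9.8 | 4.8 | 49% |
| 30% | 50% | 2% | 16.7 | 14.7 | 88% |
| 50% | 90% | 2% | 46.1 | 44.1 | 96% |

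False positives run from about 0.5 to 44 per 100 infants. The bias is upward whenever m × t > 0 and shrinks as maternal antibody wanes and t falls toward 0. In the third row, removing positives explained by maternal antibody would take the count from 16.7 to about 2.0 per 100.

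**The case against.** **The endpoint is minor and its table is not laid out.** It is one of two measures under an exploratory objective in a descriptive study with no hypothesis tests, and the methods sections specify no infant N-serology table. This stands and limits the weight of the point. It does not rescue the definition, which already states what is to be counted.

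**A reader might infer that the infant count will be mainly maternal seroprevalence, or that infections are being invented.** The documents do not support that. They give no maternal N-seroprevalence and no transfer rate. Section 5.7.1.1 names S-ELISA, psVNA and MSD 4-plex for infants, in an open-ended list, so N testing of cord blood is not confirmed. Section 5.7.1.5.1 speaks of binding antibody generally; that anti-N antibody behaves likewise is a reasonable inference, not a statement in the SAP. The false share in the illustration spans 9% to 96%.

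**A reader might also extend the fault to adults.** That largely fails. Section 5.7.2 gives seroconversion as the purpose of the adult test, and the table it adds shows N-positivity by time point without calling it infection. The Section 5.7.3.2 table is limited to the baseline-seronegative. Recipients of inactivated vaccines fall outside that group, because Table 7 makes them not evaluable: "Since participant is previously vaccinated with an inactivated vaccine, it is not possible to determine serostatus at baseline". Only the adult bullet in Section 5.5.1 is looser than these sections.

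**Could Section 5.7.3.2 already cover infants?** The SAP sometimes uses the word participant for infants too, so this reading is possible. But the table sits in the section on symptom reporting, and its serostatus definition does not fit infants.

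**Conclusion.** The point holds for infants. The serology measure equates N-seropositivity with the infant's own infection, and nothing in the SAP clearly repairs it. The error is false-positive misclassification, confined to infants who still carry maternal anti-N antibody and greatest in cord blood and early samples. Its size cannot be derived from the SAP; 0.5 to 44 per 100 infants is an illustration resting on the assumed m, t and q. Primary and secondary endpoints, the RT-PCR measure and the table of molecularly confirmed infant infections are unaffected. It should still be corrected, because the stated rule gives a count biased in a known direction.

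**What to change.** **Infants.** Count a serological infection only when either:

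1. an N-negative cord or earlier infant sample is followed by an N-positive infant sample (if no such earlier sample exists, an N-negative mother at delivery may stand in for it); or
2. the N level rises by a prespecified amount between consecutive infant samples.

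Report all other N-positive infants as not evaluable, by the mother's N status at delivery. Show RT-PCR cases separately, and state the number of evaluable infants as the denominator.

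**Adults.** Align the N-serology bullet in Section 5.5.1 with the seroconversion wording of Section 5.7.2 and the baseline-seronegative restriction of Section 5.7.3.2. Nothing more is needed.

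**Cost.** SAP wording, one derivation and fewer evaluable infants. Under the model above with complete sampling, at most the infants of N-positive mothers are lost (10 to 50 per 100 for m = 10-50%), fewer if a later negative sample or a rise makes them evaluable. The rule needs N results on cord or earlier infant samples, which the SAP does not guarantee; if they are absent, those tests must be added or more infants become not evaluable. The rise criterion also needs an N assay that reports a level.

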5.5.2. Estimands

Not applicable.

5.5.3. Analysis Methods

Occurrence of symptomatic molecularly confirmed COVID-19 and severity of COVID-19 signs and symptoms.

Refer to Section 5.7.2.

Further exploration of the impact of vaccination with Ad26.COV2.S on coagulation-related parameters in adult participants.

Refer to Section 5.6.2

Neurodevelopmental status in neonates/infants

The frequency and percentage of neonates/infants who score in the "white", "gray" or "black" zones of each of the 5 developmental areas measured in the ASQ3 as well as whether pediatrician contact was advised (as recorded in the eCRF) will be summarized. A listing of ASQ3 will be provided.

All other exploratory endpoints

Refer to Section 5.7.

5.6. Other Safety Analyses

5.6.1. Adverse Events

5.6.1.1. Definitions

Solicited AEs are used to assess the reactogenicity of the study vaccine and are predefined as local events (pain/tenderness, erythema, and swelling at the injection site) and systemic events (fatigue, headache, nausea, and myalgia) for which the participant is specifically questioned, and which are noted by participants in their diary. Unsolicited AEs are all AEs for which the participant is not specifically questioned.

MAAEs are defined as AEs with medically-attended visits including hospital, emergency room, urgent care clinic, or other visits to or from medical personnel for any reason. Routine study visits will not be considered medically-attended visits. New onset of chronic diseases will be collected as part of the MAAEs.

The severity of the AEs will be classified as grade 1 to 4. Solicited events that are graded less than grade 1 are not considered as AE. In case no grades are available, the grading of the solicited events will occur according to the grading list in Section 6.6.

Suspected AESIs (thrombotic events and thrombocytopenia [defined as platelet count below 150,000/ μ L, see Brighton Collaboration Interim Case Definition, 2021] as details in Section 6.7) will be recorded from the moment of vaccination until the end of the study/early withdrawal. An AESI Adjudication Committee with appropriate expertise will be established to evaluate each suspected AESI (for more details see Section 1.3.6 and Section 8.3.5.1 of the Protocol).

